5.4.9. Criteria for Permanent Discontinuation of Study Drug

The occurrence of unacceptable toxicity not caused by the underlying malignancy will be presumed to be related to study treatment and will require that the study treatment be permanently discontinued. Unacceptable toxicity is defined as follows:

- Grade 4 or life-threatening AEs, except with approval from the medical monitor.
- \geq Grade 2 ocular irAE.
- Occurrence of an AE that is related to treatment, in the judgment of the investigator or the medical monitor, and compromises the subject's ability to continue study-specific procedures or is considered to not be in the subject's best interest.
- Persistent AE requiring a delay of treatment for more than 4 weeks (28 days) unless a greater delay has been approved by the sponsor.

5.5. Withdrawal of Subjects From Study Treatment

5.5.1. Withdrawal Criteria

A subject may choose to withdraw from the study treatment at any time or be withdrawn from the study treatment by the investigator or sponsor, if the subject is noncompliant with the study requirements. If permanent discontinuation of any of the study treatments is necessary (eg, INCAGN01876, nivolumab, ipilimumab), all study treatments, will be discontinued. If a subject is withdrawn from study treatment, then every reasonable effort should be made to determine the reason for withdrawal, and this information should be recorded in the eCRF.

Subjects **must** be withdrawn from **study treatment** for the following reasons:

- The subject becomes pregnant.
- Consent is withdrawn. Subjects may choose to withdraw from the study at any time without penalty of jeopardizing their health care or loss of benefits to which the subject is otherwise entitled.

Note: Consent withdrawn means that the subject can no longer be followed and no additional data can be collected. Subjects may choose to discontinue study treatment and remain in the study to be followed for progression and survival.

Note: As of Protocol Amendment 5, subjects who withdraw consent will no longer be followed for progression and survival beyond the last safety follow-up visit.

- Further participation would be injurious to the subject's health or well-being, in the investigator's medical judgment.
- Unacceptable toxicity (see Section 5.4.9). Subjects with unacceptable toxicities must be withdrawn from study treatment but will continue in the follow-up phase of the study (see Section 6.4).
- The study is terminated by the sponsor.
- The study is terminated by the local health authority, IRB, or IEC.

A subject **may** be discontinued from **study treatment** as follows:

- Confirmed radiographic progression of disease per RECIST v1.1 (see Section 7.7.1). A subject may be granted an exception to continue on treatment with confirmed radiographic progression if clinically stable or clinically improved (see Section 7.7.1).
Note: For unconfirmed progression see Section 7.7.1.
- If, during the course of the study, a subject is found not to have met eligibility criteria (see Section 3), the medical monitor, in collaboration with the investigator, will determine whether the subject should be withdrawn from the study.
- If a subject is lost-to-follow-up or noncompliant with study procedures or study treatment in the investigator's opinion, the sponsor should be consulted for instruction on handling the subject.

5.5.2. Withdrawal Procedures

In the event that the decision is made to permanently discontinue the study treatment, the subject will be withdrawn, and the EOT visit should be conducted. Reasonable efforts should be made to have the subject return for all applicable follow-up visits (safety and efficacy; see Section 6.4). The last date of the last dose of study treatment and the reason for subject withdrawal will be recorded in the eCRF.

If a subject is withdrawn from the study treatment:

- The study monitor or sponsor must be notified.
- The reason(s) for withdrawal from treatment must be documented in the subject's medical record and in the eCRF.

Note: The reason for withdrawal from treatment may be different than the reason for withdrawal from study. For example, subjects can discontinue treatment for disease progression or toxicity, but remain in the study for safety and survival follow-up.

Note: As of Protocol Amendment 5, subjects who discontinue treatment will no longer be followed for progression and survival beyond the last safety follow-up visit.

- The EOT visit should be performed.
- The date of the EOT visit should be recorded in the eCRF and IRT.
- Subjects must be followed for safety until the time of the follow-up visit or until study treatment-related toxicities resolve, return to baseline, or are deemed irreversible, or until the subject begins new anticancer therapy, whichever is longest.
- Subjects who discontinue for reasons other than disease progression will continue to be followed for disease status as outlined in Section 6.4.2.

Note: As of Protocol Amendment 5, subjects who discontinue for reasons other than disease progression will no longer be followed for disease status beyond the last safety follow-up visit.

- All subjects who discontinue study treatment will continue to be followed for OS as outlined in Section 6.4.3.

Note: As of Protocol Amendment 5, subjects who discontinue study treatment will no longer be followed for survival beyond the last safety follow-up visit.

If the subject discontinues study treatment and actively withdraws consent for collection of follow-up data (safety follow-up, disease assessments, or survival follow-up), then no additional data collection should occur; however, **subjects will have the option of withdrawing consent for study treatment but continuing in the follow-up period of the study for safety, efficacy, and survival assessments.**

Note: As of Protocol Amendment 5, subjects who withdraw consent but continue in the follow-up period will be followed for efficacy and survival until the last safety follow-up visit.

5.6. Concomitant Medications

All concomitant medications and treatments must be recorded in the eCRF. Any prior medication received up to 28 days before the first dose of study treatment and 60 days after the last dose of study treatment, or until the subject begins a new anticancer therapy, whichever occurs first, will be recorded in the eCRF. Any addition, deletion, or change in the dose of these medications will also be recorded. Concomitant treatments/procedures that are required to manage a subject's medical condition during the study will also be recorded in the eCRF.

5.6.1. Permitted Medications

All treatments that the investigator considers necessary for a subject's welfare may be administered at the discretion of the investigator in keeping with the community standards of medical care. All concomitant medications will be recorded on the eCRF, including all prescription, over-the-counter, herbal supplements, and IV medications and fluids. If changes occur during the study period, documentation of drug regimen, frequency, route, and date may also be included on the eCRF. *Note:* The use of bisphosphonates and denosumab are permitted in this study.

5.6.2. Restricted Medications

Systemic glucocorticoids for any purpose other than prophylaxis for contrast allergies for radiographic procedures, or to modulate symptoms or treat an AE of suspected immunologic etiology, are restricted and require medical monitor approval. The use of physiologic corticosteroid replacement therapy may be approved after consultation with the medical monitor.

Note: Inhaled and topical steroids are allowed. A short course of steroids (prednisone or equivalent) ≤ 10 mg/day may be permitted with medical monitor approval.

5.6.3. Prohibited Medications

Medications or vaccinations specifically prohibited in the exclusion criteria (see Section 3.2) are not allowed during the study. If there is a clinical indication for one of these medications or vaccinations specifically prohibited during the study, discontinuation from study treatment may be required. The investigator should discuss any questions regarding this with the medical monitor. The final decision on any supportive therapy or vaccination rests with the investigator

and/or the subject's primary physician. However, the decision to continue the subject on study treatment requires the mutual agreement of the investigator, the sponsor, and the subject.

Subjects are prohibited from receiving the following therapies during the screening and treatment periods of this study, unless otherwise indicated:

- Any anticancer medications, including chemotherapy or biologic therapy other than study treatment.
- Any immunological-based treatment for any reason from screening through the safety follow-up visit is prohibited.

Note: Completed adjuvant therapy (eg, vaccines) with medical monitor approval, inhaled or topical steroids, systemic steroids at doses ≤ 10 mg/day prednisone or equivalents, and immune suppressants are allowed for treatment for immune toxicities as described in Section 5.4.7 and Appendix B, or as prophylaxis for contrast allergy for imaging procedures.

Note: Allergy shots may be permitted after consultation with the medical monitor.

- Investigational agents other than study treatment. Use of such medications from screening through the safety follow-up visit is prohibited.
- Concomitant radiation therapy.

Note: Radiation therapy to a symptomatic solitary lesion or to the brain may be considered on an exceptional case-by-case basis after consultation with the medical monitor. The subject must have clear measurable disease outside the radiated field. Administration of palliative radiation therapy will be considered clinical progression for the purposes of determining PFS.

- Live vaccines within 30 days before the first dose of study treatment and while participating in the study. Examples of live vaccines include, but are not limited to, the following: measles, mumps, rubella, chicken pox, yellow fever, rabies, Bacillus Calmette–Guérin, and typhoid (oral) vaccine. Seasonal influenza vaccines for injection are generally killed virus vaccines and are allowed. However, intranasal influenza vaccines are live attenuated vaccines and are not allowed.

Subjects who, in the assessment by the investigator, require the use of any of the aforementioned treatments for clinical management should be removed from the study. Subjects may receive other medications that the investigator deems to be medically necessary. The exclusion criteria describe other medications that are prohibited in this study. There are no prohibited therapies during the post-treatment follow-up period.

6. STUDY ASSESSMENTS

All study assessments will be performed as indicated in the schedule of clinical assessments (Table 10), and all laboratory assessments will be performed as indicated in Table 11. Table 12 presents a summary of clinical laboratory analytes to be assessed. The order of assessments is suggested by the order of mention within the schedule. See Section 7 for instructions on each assessment. Further details of study procedures and assessments can be found in the study reference manual or applicable procedural documentation.

Table 10: Schedule of Clinical Assessments

Visit Day (Range)	Protocol Section	Screening	Treatment ^a				Post-Treatment ^b			
			Cycles 1 and 6		All Other Cycles	Every 8 weeks	EOT	Safety Follow-Up Visit 1 ^c	Safety Follow-Up Visit 2 ^c	Survival Follow-Up ^d
			Day 1	Day 8	Day 1	Disease Status				
Evaluation/Window		Day -28 to -1	± 3 days ^e	± 1 day	± 3 days	± 7 days	± 3 days	30 days (+ 7 days)	60 days (+ 7 days)	Every 12 weeks (± 7 days)
Administrative procedures										
Informed consent	7.1	X								
Inclusion/exclusion criteria	3.1, 3.2	X	X							
Contact IRT	7.2	X	X		X		X			
Medical and cancer history	7.3.1 7.3.2	X								
Prior/concomitant medications	7.4	X	X	X	X		X	X	X	
Administer INCAGN01876	5.2.1.1		X ^f		X ^f					
Administer nivolumab	5.2.2.1		X ^g		X ^g					
Administer ipilimumab	5.2.2.2		X ^h		X ^h					
Poststudy anticancer therapy status	7.5							X	X	
Survival status	6.4.3									X
Clinical procedures/assessments										
Comprehensive physical examination (including height)	7.6.2.1	X								
Targeted physical assessment	7.6.2.2		X	X ⁱ	X		X	X	X	
Vital signs and weight	7.6.3	X	X	X ⁱ	X		X	X	X	
ECOG performance status	7.8.1	X	X	X ⁱ	X		X	X	X	
Laboratory assessments	7.6.5	X	X	X	X		X	X	X	
12-lead ECG ^j	7.6.4	X					X	X		
AE assessment	7.6.1	X	X	X ⁱ	X		X	X	X	
Efficacy measurements										
Radiologic tumor assessments	7.7	X ^k					X ^l	X ^m	X ⁿ	

^a Treatment cycles will be Q2W (14 days ± 3 days). Alternate dose administration schedules and/or fixed doses of INCAGN01876 (comparable to or less than the highest dose levels determined to be safe or pharmacologically active), may also be explored depending on [REDACTED] safety results.

^b The mandatory safety follow-up visits should be conducted approximately 30 days and 60 days after the last dose of study treatment or before the initiation of a new anticancer treatment, whichever comes first.

^c As of Protocol Amendment 5, the safety follow-up visits will include AE and concomitant medication assessment only and may be completed remotely (such as by televisit).

- ^d As of Protocol Amendment 5, no further survival follow-up assessment will be required beyond the last safety follow-up visit.
- ^e Evaluation window only applies to Cycle 6 Day 1.
- ^f In Treatment Group B, INCAGN01876 is only administered on Day 1 of Cycles 1 and 2.
- ^g In Treatment Groups B, E, H, and L, nivolumab administration begins at Cycle 3 Day 1.
- ^h For subjects enrolled into Treatment Groups C and C2 (INCAGN01876 + ipilimumab) and Treatment Groups D and J (INCAGN01876 + nivolumab + ipilimumab), ipilimumab will be administered on Cycle 1 Day 1 and then Day 1 of every 3rd cycle (Cycle 1, Cycle 4, Cycle 7, etc). In Treatment Groups E and L ipilimumab administration begins at Cycle 3 Day 1 and then continues on Day 1 of every third cycle. If higher doses of ipilimumab are tested (eg, 3 mg/kg every 3 weeks [21 days] for 4 doses), then ipilimumab will be administered on Day 1 of each 3-week (21-day) cycle for a total of 4 doses. If the scheduled ipilimumab doses fall on days other than Day 1 of a cycle, the subjects will need to be present in clinic for the infusion, and any standard procedures required by the site should be performed.
- ⁱ Applicable to all subjects at Cycle 1 Day 8. At Cycle 6 Day 8, only required if subject is experiencing AEs > Grade 2.
- ^j All 12-lead ECGs will be performed with the subject in a recumbent or semirecumbent position after 5 minutes of rest and should not be performed within 15 minutes after a blood collection. ECGs will be collected at screening and at least every 8 weeks, or as clinically indicated per prescribing instructions for nivolumab, as well as the EOT and first safety follow-up visits.
- ^k The initial tumor imaging will be performed within 28 days before the first dose of study treatment. Images of the chest, abdomen, and pelvis are required for all subjects. Scans performed as part of routine clinical management are acceptable for use as the screening scan if they are of diagnostic quality and performed within 28 days before the first dose of study treatment. The same imaging technique should be used for a subject throughout the study. Local reading (investigator assessment with site radiology reading) will be used to determine eligibility and for subject management.
- ^l On-study imaging will be performed at Week 8 and then every 8 weeks (± 7 days) for the first 12 months and then every 12 weeks (± 7 days) thereafter. Imaging should follow calendar days starting with Day 1 of INCAGN01876 treatment and should NOT be adjusted for delays in cycle starts. If imaging shows disease progression, then another imaging assessment should be performed at a minimum of 4 weeks but no later than 6 weeks later to confirm progression per mRECIST.
- ^m If scan was obtained within 4 weeks before the date of discontinuation, then a scan at treatment discontinuation (EOT) is not mandatory. For subjects who discontinue study therapy without confirmed disease progression, a radiologic evaluation should be repeated at the time of treatment discontinuation (ie, date of discontinuation ± 4 week window).
- ⁿ For subjects who discontinue treatment for reasons other than disease progression, every effort should be made to continue monitoring their disease status every 8 weeks (± 7 days) by radiographic imaging until 1) start of new anticancer therapy, 2) documented disease progression, 3) death, 4) the end of the study, or 5) withdrawal of consent, whichever occurs first.
- Note:** As of Protocol Amendment 5, no further disease status follow-up assessments will be required beyond the last safety follow-up visit.

Table 11: Schedule of Laboratory Assessments

Visit Day (Range)	Protocol Section	Timing of Assessment	Screening Day -28 to -1	Treatment										Post-Treatment			
				C1		C2	C3	C4	C6		C7	Every 4th Cycle (C8, C12)	All Other Cycles	EOT	Safety Follow-Up Visit 1	Safety Follow-Up Visit 2	
				D1	D8	D1	D1	D1	D1	D8	D1	D1	D1				
Evaluation/Window					± 1 day	± 3 days	± 3 days	± 3 days	± 3 days	± 3 days	± 3 days	± 3 days	± 3 days	± 3 days	± 3 days	30 days (+ 7 days)	60 days (+ 7 days)
Local laboratory tests^a																	
Comprehensive serum chemistries ^b	7.6.5	N/A	X ^c	X ^d	X	X	X	X	X	X	X	X	X	X	X	X	X
Hematology with differential	7.6.5	N/A	X ^c	X ^d	X	X	X	X	X	X	X	X	X	X	X	X	X
Coagulation panel ^e	7.6.5	N/A	X ^c														
Urinalysis	7.6.5	N/A	X ^c											X			
Endocrine function tests	7.6.5	N/A	X ^c					X					X	X			
Hepatitis B and C	7.6.5.2	N/A	X														
Serum pregnancy test (childbearing females only) ^f	7.6.5.1	N/A	X											X			
Urine pregnancy test (childbearing females only)	7.6.5.1	N/A			X ^g												

- ^a All safety laboratory assessments will be performed locally.
- ^b If liver chemistry tests increase in grade from baseline or are \geq Grade 3, then liver chemistry monitoring should increase to once per week until resolved to baseline or \leq Grade 1. Liver chemistry does not need to be monitored once per week indefinitely for persistent low grade abnormalities. Appropriate liver chemistry monitoring intervals should be discussed with the medical monitor for these circumstances.
- ^c Screening laboratory tests must be performed within 7 days of Cycle 1 Day 1. If performed more than 7 days before Cycle 1 Day 1, then the tests must be repeated and eligibility confirmed before study treatment administration on Cycle 1 Day 1.
- ^d Only required to be performed at Cycle 1 Day 1 if the screening assessment was not performed within 7 days.
- ^e Subjects on anticoagulation treatment should have parameters monitored throughout the study as clinically indicated.
- ^f A serum pregnancy test will be required for all women of childbearing potential during screening and must be within 72 hours before the first dose of study treatment.
- ^g Urine pregnancy tests will be conducted as medically indicated or per country-specific requirements (see Section 7.6.5.1).

█ [REDACTED]

ⁱ Collected only on Cycle 8 Day 1 and Cycle 12 Day 1.

j [REDACTED]

Table 12: Local Laboratory Tests: Required Analytes

Serum Chemistries	Hematology	Urinalysis	Hepatitis Screening ^a	Coagulation	
Albumin	Complete blood count, including: 
 • Hemoglobin • Hematocrit • Platelet count • Red blood cell count • White blood cell count 	Color and appearance pH and specific gravity Bilirubin Glucose Ketones Leukocytes Nitrite Occult blood Protein	HBsAg	PT aPTT INR	
Alkaline phosphatase			anti-HBc antibody		
ALT	Absolute values must be provided for WBC differential laboratory results: 
 • Basophils • Eosinophils • Lymphocytes • Monocytes • Neutrophils 		HBV-DNA	Pregnancy Testing Female subjects of childbearing potential only require a serum test at screening and EOT. Pregnancy tests (serum or urine) should be repeated if required by local regulations.	Endocrine Monitoring Thyroid-stimulating hormone (TSH) Free thyroxine (T4) Total triiodothyronine (T3)/FT3 ^b
AST					
Bicarbonate or CO ₂					
Blood urea nitrogen or urea					
Calcium					
Chloride					
Creatinine					
Glucose					
Lactate dehydrogenase					
Phosphate					
Potassium					
Sodium					
Total bilirubin					
Direct bilirubin (if total bilirubin is elevated above ULN)					
Total protein					
Uric acid					
Amylase					
Lipase					

^a No HCV-RNA test is required in case HCV antibody test result is negative. No HBV DNA test is required in case HBsAg and anti-HBc antibody testing are negative.

^b If considered standard by your region.

6.1. Screening

Screening is the interval between signing the ICF and the day the subject is enrolled in the study (eg, Cycle 1 Day 1). Screening may not exceed 28 days. Informed consent must be obtained before performing any study-specific procedures that are not considered standard of care; however, procedures conducted as part of the subject's routine clinical management obtained before signing of informed consent may be used for screening or baseline purposes with approval of the medical monitor, provided that the procedure meets the Protocol-defined criteria and has been performed in the timeframe of the study. Assessments that are required to demonstrate eligibility may be performed over the course of 1 or more days during the screening process.

Results from the screening visit evaluations will be reviewed to confirm subject eligibility before enrollment. Tests with results that fail eligibility requirements may be repeated **once** during screening if the investigator believes the results to be in error. For screening assessments that are repeated, the most recent available result before enrollment will be used to determine subject eligibility. Additionally, a subject who fails screening may repeat the screening process **1 time** if the investigator believes there has been a change in eligibility status (eg, after recovery from an infection). Treatment should start as soon as possible after the date of enrollment.

6.2. Treatment

The treatment period begins on the day the subject receives the first dose of study treatment (Cycle 1 Day 1) through the point at which the investigator determines that the subject will be permanently discontinued from study treatment, or for up to 24 months from the first dose of study treatment, whichever occurs first. Cycle 1 Day 1 must be no more than 28 days after the subject has signed the ICF and should be within 3 days of enrollment in the study. Subjects will have regularly scheduled study visits as outlined in [Table 10](#) and toxicities will be monitored continuously and will be graded using the NCI CTCAE v4.03 criteria.

6.3. End of Treatment

When the subject permanently discontinues study treatment, the EOT visit should be conducted. If the EOT visit coincides with a regular study visit, the EOT evaluations will supersede those of that scheduled visit, and the data should be entered in the EOT visit in the eCRF. The subject should be encouraged to return for the safety and survival follow-up visits.

Note: As of Protocol Amendment 5, subjects who permanently discontinue study treatment will no longer be followed for survival beyond the last safety follow-up visit.

6.4. Follow-Up

6.4.1. Safety Follow-Up

The safety follow-up period is the interval between the EOT visit and the scheduled follow-up visit, which should occur 30 days (+ 7 days) and 60 days (+ 7 days) after the last dose of study treatment. Monitoring for the occurrence of new AEs should be continued for at least 60 days after the last dose of study treatment or until the start of new anticancer therapy, whichever occurs first. Reasonable efforts should be made to have the subject return for the follow-up visits and report any AEs that may occur during this period. If a subject is scheduled to begin a new anticancer therapy before the end of the 30-day or 60-day safety follow-up period, the safety follow-up visit should be performed before new anticancer therapy is started. Once new anticancer therapy has been initiated, AEs and SAEs will no longer be collected, and the subject will move into the survival follow-up period.

Note: As of Protocol Amendment 5, the safety follow-up visits will include AE and concomitant medication assessment only and may be completed remotely (such as by televisit).

Note: As of Protocol Amendment 5, if a new anticancer therapy has been initiated before the end of the safety follow-up period, no further survival follow-up assessment will be required beyond the last safety follow-up visit.

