5.4.7. Management of Immune-Related Adverse Events

INCAGN01876, nivolumab, and ipilimumab are considered immune modulators, and it is possible that irAEs (both nonserious and serious) may occur. Adverse events of a potential immunologic etiology or irAEs may be defined as an AE consistent with an immune phenomenon associated with drug exposure *after all other etiologies have been eliminated*. Immune-related AEs may be expected based on the nature of the study treatment, their mechanism of action, and reported experience with these and other immunotherapies. Special attention should be paid to AEs that may be suggestive of potential irAEs. An irAE can occur shortly after the first dose or several months after the last dose of treatment. Suspected irAEs should be discussed with the medical monitor when possible.

Subjects should receive appropriate supportive care measures as deemed necessary by the treating investigator. Suggested supportive care measures for the management of drug-related AEs with potential immunologic etiology are outlined in [Table 8](#). Detailed supportive care guidelines for specific irAEs can be found in [Appendix B](#). Nivolumab and ipilimumab are approved therapies and have specific irAE management guidelines within their package insert; the treating investigator may use labeled guidance or institutional guidelines for the management of irAEs if preferred. For each AE, attempts should be made to rule out other causes, including but not limited to metastatic disease or bacterial or viral infection, which might require specific supportive care.

Table 8: Supportive Care Guidelines for Immune-Related Adverse Events

CTCAE Grade/Severity	Supportive Care ^a
Grade 1 (mild)	
 • Monitor symptoms and provide symptomatic treatment.
Grade 2 (moderate)	
 • Monitor symptoms and provide symptomatic treatment. • Consider consultation with specialists as necessary. • Consider systemic corticosteroids per institutional standard of care.

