8.3.2. Reporting

Every SAE, regardless of suspected causality (eg, relationship to study drug(s) or study procedure or disease progression), occurring after the subject has signed the ICF through the last study visit (or 60 days after the last dose of study treatment, or until the subject receives a new anticancer therapy whichever occurs earlier) must be reported to the sponsor (or designee) within **24 hours** of learning of its occurrence, unless otherwise specified by the Protocol. Any SAEs occurring more than 60 days after the last dose of study treatment should be reported to the sponsor or its designee only if the investigator suspects a causal relationship to the study drug.

Information about all SAEs is collected and recorded on the Adverse Event form of the eCRF. The investigator must assess and record the causal relationship of each SAE to each specific study treatment. The investigator must also complete the Incyte Serious Adverse Event Report Form, in English, and send the completed and signed form to the sponsor or designee within 24 hours of becoming aware of the SAE. The investigator must provide a causality assessment, that is, assess whether there is at least a reasonable possibility that the SAE is related to the specific study treatment: suspected (yes) or not suspected (no). Refer to the Incyte Reference Guide for Completing the Serious Adverse Event Report Form.

The contact information of the sponsor's study-specific representatives is listed in the investigator manual provided to each site. The original copy of the SAE Report Form and the confirmation sheet must be kept at the study site.

Investigational site personnel must report any new information regarding the SAE within 24 hours of becoming aware of the information in the same manner that the initial SAE Report Form was sent. Follow-up information is recorded on an amended or new SAE Report Form, with an indication that it is follow-up to the previously reported SAE and the date of the original report. The follow-up report should include information that was not provided on the previous SAE Report Form, such as the outcome of the event (eg, resolved or ongoing), treatment provided, action taken with study drug because of the SAE (eg, dose interrupted or discontinued), or subject disposition (eg, continued or withdrew from study participation). Each recurrence, complication, or progression of the original event should be reported as follow-up to that event.

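### Section 8.3.2 sets no reporting duty for a suspected-related SAE that begins after a switch to new anticancer therapy and by Day 60, and Sections 6.4.1, 5.5.2 and 8.1.2 do not agree on when safety collection ends

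*Protocol*

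**What the plan says.** All day numbers here count from the last dose of study treatment.

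- **Protocol 8.3.2, first rule.** Every SAE, whatever its cause, is reported within 24 hours of the site learning of it. The window runs to the last study visit, with the limit "or 60 days after the last dose of study treatment, or until the subject receives a new anticancer therapy whichever occurs earlier".
- **Protocol 8.3.2, second rule.** "Any SAEs occurring more than 60 days after the last dose of study treatment should be reported", but "only if the investigator suspects a causal relationship to the study drug".
- **Protocol 6.4.1.** New AEs are monitored for at least 60 days or until new anticancer therapy, taking the first of the two. It then adds: "Once new anticancer therapy has been initiated, AEs and SAEs will no longer be collected". There is no exception for related events and no end date.
- **Protocol 8.1.2.** It uses the same first-of-two limit for AE monitoring. An AE already detected is followed until it resolves or is judged permanent.
- **Protocol 5.5.2.** Subjects are followed for safety until the follow-up visit, the settling of treatment-related toxicity, "or until the subject begins new anticancer therapy, whichever is longest".
- **Protocol 5.4.7.** "An irAE can occur shortly after the first dose or several months after the last dose of treatment".
- **Protocol 5.2.1.1.** The study drug is INCAGN01876.
- **SAP.** It contains no SAE reporting rule.

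**The concern.** The second rule in 8.3.2 should begin where the first one stops. It begins at a fixed day instead. For a subject who moves to new therapy before Day 60, the duty to report a related SAE therefore lapses at the switch and returns after Day 60. The event closer to exposure is the one left out. Confounding by the new therapy cannot be the reason, because the second rule applies after Day 60 whether or not a new therapy has started.

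The situation is foreseeable. Section 7.5 plans for new therapy at 30 to 60 days, and Section 6.4.1 plans for it before either safety visit. Section 5.4.7 expects immune-related events well after dosing ends. At stake are the sponsor's receipt of related SAEs for a new combination and the completeness of the late safety record, in subjects who leave treatment and move on quickly.

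**Working it through.** The plan gives no figure to reproduce. The check treats the rules as time intervals.

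**Inputs.** T is the day new anticancer therapy starts, with T < 60; the documents do not give it. The 60-day limit comes from 8.3.2. Let t be the onset day of an SAE that the investigator suspects is related to study treatment.

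**Coverage of a related SAE, by onset**

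| Onset | 8.3.2, first rule | 8.3.2, second rule | 6.4.1 |
|---|---|---|---|
| t ≤ T | report | not open | collected |
| T < t ≤ 60 | closed at T | not open | not collected |
| t > 60 | closed at T | report | not collected |

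The last study visit also appears in the first rule. Read as one more item in the same earliest-of comparison, it can only close the window sooner.

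**Length of the uncovered interval:** 60 - T days.

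- T = 14: 60 - 14 = 46 days
- T = 30: 60 - 30 = 30 days
- T = 45: 60 - 45 = 15 days
- No new therapy by Day 60: no gap

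These values of T are assumptions that show the range.

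**Example.** A subject switches on Day 20 and has a related SAE on Day 40. The first rule closed on Day 20 and the second has not opened. With onset on Day 61, 8.3.2 requires a report while 6.4.1 says nothing is collected.

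**Which section governs?** If 8.3.2 prevails, the gap runs from T to Day 60. If 6.4.1 prevails, it runs from T onward without end. The interval from T to Day 60 is uncovered on both readings; only the period after Day 60 depends on the choice.

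**Can another section fill it?** Section 8.1.2 follows events already detected, so it does not reach one that begins after the switch. Section 5.5.2 could keep a subject in safety follow-up during the gap, because it takes the longest of its limits, but it sets no SAE reporting duty. It also contradicts 6.4.1 and 8.1.2, which take the first.

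**Drug scope.** The second rule depends on suspicion of the study drug, which 5.2.1.1 identifies as INCAGN01876. Elsewhere 8.3.2 allows for more than one study drug and asks for causality against each study treatment. Whether a late SAE attributed only to nivolumab or ipilimumab is covered is therefore ambiguous.

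**The case against.** The strongest reply is that ending collection at new therapy is a deliberate and consistent choice: 6.4.1, 8.1.2 and the first rule of 8.3.2 all make it, since later events are hard to attribute. The safety visit is to be held before the switch, and events found by then are followed up. This stands for unrelated events, and it limits the gap to SAEs with onset after the switch. It does not explain why 8.3.2 resumes reporting of related SAEs after Day 60 but not before.

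A reader might infer more than the documents support:

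- **That such an SAE can never be reported.** The text imposes no duty and places the event outside collection. It does not forbid a voluntary report.
- **That the share of lost safety time can be estimated.** One could take the 14- and 28-day entry washouts in 3.2 as switch days and multiply the loss by an assumed share of switchers. Those washouts govern entry to this study, not later treatment. A subject switching on Day 45 loses 15 days, not 46. Neither the share nor the timing of switches is given.
- **That the Phase 2 rule on more than 40% Grade 3 or higher related AEs is impaired.** That rule interrupts enrollment, and the Amendment 5 rationale in Appendix C says enrollment is complete.
- **That ending survival contacts under Amendment 5 widens the gap.** Section 6.4.3 limits them to survival status. At 12-week intervals from the last dose, as the synopsis sets them, the first falls near Day 84 (12 × 7), after Day 60.
- **That Section 1.4 shows late liver and endocrine onset after the last dose.** It orders those events relative to skin and gastrointestinal ones. Only 5.4.7 speaks of onset after dosing ends.

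**Conclusion.** The point holds as a gap and a set of conflicts in the wording. For any subject who starts new anticancer therapy on Day T < 60, the protocol sets no duty to report a suspected-related SAE with onset in the following 60 - T days. This follows from 8.3.2 alone, and 6.4.1 reinforces it. Two further inconsistencies go with it: 6.4.1 against the second rule of 8.3.2 after Day 60, and 5.5.2 against 6.4.1 and 8.1.2. The drug scope of the late rule is ambiguous rather than clearly exclusive.

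The length of the gap for one subject is arithmetic once T is known. The number of subjects and events affected cannot be derived from the documents. The correction should be made: the events concerned are ones the protocol expects, and the change is small.

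**What to change.** - **8.3.2:** open the second rule when the first window closes, at Day 60 or new anticancer therapy, whichever is earlier. Word it as suspected relationship to any study treatment: INCAGN01876, nivolumab or ipilimumab.
- **6.4.1:** add the matching exception for suspected-related SAEs. Keep the new-therapy cut-off for unrelated events.
- **5.5.2 and 8.1.2:** reconcile the longest-of and first-of limits with each other and with 6.4.1.
- **AE listing:** flag events with onset after new anticancer therapy, so they can be read separately.

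The cost is protocol wording, one listing flag and a few more SAE reports. Some of those will be confounded by the new therapy; the flag makes that visible but does not remove it.
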